## 9.2 SAMPLE SIZE DETERMINATION

Statistical power analysis is not relevant for estimating person-specific dynamic models. Our proposed sample size (n=80) is based on the upper limit for phase 1 clinical trials and will enable us to capture the heterogeneity of PA dynamics and estimate model uncertainty within the resource constraints of early stage intervention development work.

## 9.3 POPULATIONS FOR ANALYSES

All study completers will be analyzed.

## 9.4 STATISTICAL ANALYSES

### 9.4.1 GENERAL APPROACH

The steady state response (i.e., final cumulative response) to each type of intervention message will be recorded as the primary outcome variable. The mean and standard deviation of steady state responses will be calculated.

### 9.4.2 ANALYSIS OF THE PRIMARY ENDPOINT(S)

System identification will be used to estimate coefficients for person-specific dynamic models of moderate-to-vigorous physical activity durations in 15-minute epochs. Model coefficients will be used to simulate expected responses to each type of micro-intervention (separately for weekdays and weekends). Steady state responses for each message type on weekdays and weekends will be extracted as the primary outcome. An independent-sample t-test will be used to evaluate whether the average steady state response to each message type on weekdays and weekends differs significantly from zero.

---

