## 1 PROTOCOL SUMMARY

### 1.1 SYNOPSIS

[figure not shown]
Title:	Random Assignment of Intervention Messages for Developing Personalized Decision Rules to Promote Physical Activity
Grant Number:	R01 HL142732
Study Description:	This study aims to develop a method for characterizing the dynamics of person-specific behavioral responses of a behavioral intervention. Our long-term goal is to evaluate a personalized adaptive messaging intervention for PA based on dynamical models of historical responses to intervention (and other inputs such as weather).
Objectives*:	Primary Objective: The aim of this project is to develop personalized dynamical models of physical activity (PA) under different weather and temporal conditions.
Endpoints*:	Primary Endpoint: change in minutes of moderate-to-vigorous physical activity following each of three types of micro-interventions on weekdays and weekends
Study Population:	80 female and male adults aged 18-29 years from the United States who engage in insufficient physical activity
Phase* or Stage:	Phase 1
Description of Sites/Facilities Enrolling Participants:	N/A
Description of Study Intervention/Experimental Manipulation:	Baseline education and self-regulatory training; provision of smartwatch that provides ad libitum behavioral feedback throughout study; 0-6 micro-intervention messages/day for 6 months
Study Duration*:	18 months
Participant Duration:	6 months

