## 2 INTRODUCTION

### 2.1 STUDY RATIONALE

Just-in-time adaptive interventions are a new strategy for delivering interventions to patients at moments when they are receptive and have an opportunity (or vulnerability) for behavior change. These interventions are often delivered using technology to reach people in the natural context of their daily lives. They require decision rules to specify which interventions are delivered, when they are delivered, and how often they are delivered. Our prior results raise questions about the sufficiency of a single decision rule for diverse populations. Those results showed that different people respond to different message content, responses varied on weekends and weekdays, and the timing and magnitude of responses varied. We seek to extend these results by collecting data on a larger sample of participants and enriching the model with additional data to reduce uncertainty. We focus on location-specific weather indices to enrich our models. Extensive data link physical activity with weather but, to the best of our knowledge, weather indices have never been used to inform physical activity intervention delivery. We will determine whether behavioral responses to text messages vary, for example, on sunny vs cloudy days, warm vs cool days, or rainy vs dry days. To achieve this aim, we need to collect intensive longitudinal data on behavioral responses to text messages under a variety of weather conditions.

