## 4 STUDY DESIGN

### 4.1 OVERALL DESIGN

This single-site trial is in Phase 1 of behavioral intervention development with the goal of developing a method for optimizing person-specific intervention dosing to promote health-enhancing physical activity. To test the null hypothesis that each message type will not lead to increased moderate-to-vigorous physical activity, we use a within-person randomized trial design. All participants received 0-6 messages/day drawn from three content libraries (Move More, Sit Less, Inspirational Quotes). The number of messages and content source for each message was determined randomly for each participant every day. The allocation ratio was set so participants would receive approximately 40% Move More messages, 40% Sit Less messages, and 20% Inspirational Quote messages. Randomization was conducted automatically by custom software developed to deliver messages. This intervention is referred to as Random Assignment of Intervention Messages (Random AIM).

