### 9 STATISTICAL CONSIDERATIONS

## 9.1 STATISTICAL HYPOTHESES

*State the formal and testable null and alternative hypotheses for primary and key secondary endpoints, specifying the type of analysis (e.g., feasibility/acceptability, efficacy, effectiveness, implementation) and time period for which each endpoint will be analyzed. Include this information for each hypothesis being tested, if multiple hypotheses are present. If the study is intended as a feasibility or pilot study, please consider that a formal hypothesis may not be available at the time of protocol writing. If so, include a statement indicating that hypotheses will be generated or that descriptive statistics only will be calculated.*

- Primary Endpoint(s): change in moderate-to-vigorous intensity physical activity following receipt of a message from each content library.

We hypothesize that, compared to behavior that would be expected based on the dynamic model without message delivery, patients who receive a Move More or Sit Less Message will have a positive steady state response for moderate-to-vigorous physical activity duration following message delivery. Alternatively, our null hypothesis is that there will be no difference in moderate-to-vigorous physical activity steady state responses following Move More or Sit Less messages.

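### Section 9.4.2 names no time-of-day baseline, so if messages are sent in only part of the day, the tests against zero can absorb hour-of-day differences in activity, in either direction

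*Combined protocol and SAP*

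**What the plan says.** Section 9.4.2 uses system identification to fit "person-specific dynamic models of moderate-to-vigorous physical activity durations in 15-minute epochs". The fitted coefficients are used to simulate the response to each library, separately for weekdays and weekends. A t-test then evaluates "whether the average steady state response to each message type on weekdays and weekends differs significantly from zero". Section 9.1 defines the hypothesised response as "compared to behavior that would be expected based on the dynamic model without message delivery". Section 9.4.1 adds: "The mean and standard deviation of steady state responses will be calculated".

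On time, the synopsis (section 1.1) aims to "develop personalized dynamical models of physical activity (PA) under different weather and temporal conditions". Section 9.4.2 itself mentions only the weekday/weekend split. The available text does not say which of the day's epochs enter the model or how unworn epochs are handled.

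On randomisation, section 4.1 says "we use a within-person randomized trial design", and then: "The number of messages and content source for each message was determined randomly for each participant every day". Section 6.3 describes automated delivery on a random schedule. Neither section gives the hours in which a message could be sent.

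On the outcome, section 8.1 asks for Fitbit wear while awake and counts minutes at 100 or more steps. Read literally, a sleeping or unworn minute scores zero.

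**The concern.** The tests against zero are only as good as the no-message prediction behind them. Randomising how many messages a person gets in a day, and from which library, makes days comparable and libraries comparable. It does not make one hour comparable with another. An epoch-level model without clock time builds its baseline from all analysed no-message epochs, including hours in which no message could have been sent. If those hours are less active than the sending hours, every library appears to work. If they are more active, a real effect can be hidden or reversed.

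At stake is the reading of the primary result: a response that differs from zero could not be told apart from a daily activity rhythm. The planned mean and SD for all three libraries would let a reader notice a shift common to all of them, but would not remove it.

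**Working it through.** The plan states no effect size, SD or bias figure on this point, so there is nothing to reproduce. The check is whether a model with only the named time factor returns zero when the true effect is zero.

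**Inputs from the documents.** 80 people; 15-minute epochs (96 per 24 h); 0-6 messages a day; content split 40/40/20; 6 months. A mean of 3 messages a day agrees with section 5.5: ($85 - $40)/$0.25 = 180 paid messages per two months, or about 3 a day. Exclusion criterion 1 caps screening activity at 150/7 = 21.4 min/day.

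**Assumed.** Delivery hours; waking hours 07:00-23:00 (64 epochs); activity profiles; a lower limit of 10 min/day (simulated mean about 15.6); model order; the same zero response for everyone.

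**Hand calculation.** Under no effect, the apparent effect in one epoch is (mean activity in message epochs) - (mean activity in no-message epochs). Take 15.6 min/day and 3 messages.

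- *Half activity in the first and last 2 waking hours, delivery 09:00-21:00.* The full rate r satisfies 48r + 16(r/2) = 56r = 15.6, so r = 0.279 and the half rate is 0.139. No-message mean = (15.6 - 3 × 0.279)/(64 - 3) = 0.242. Apparent effect = 0.279 - 0.242 = **+0.037 min**.
- *Same profile, delivery only in the half-rate hours.* No-message mean = (15.6 - 3 × 0.139)/61 = 0.249. Apparent effect = 0.139 - 0.249 = **-0.110 min**.
- *Flat waking activity, night epochs counted as zero, delivery in waking hours.* Waking rate = 15.6/64 = 0.244. No-message mean = (15.6 - 3 × 0.244)/(96 - 3) = 0.160. Apparent effect = **+0.084 min**.
- *Delivery spread evenly over all analysed epochs.* Both means equal the overall mean, so the apparent effect is **0**. Comparing like hour with like hour also gives 0.

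**Simulation with a dynamic model.** 20 trials per scenario, 182 days, least squares per person, 2 activity lags and 2 h of message lags. Steady state = (sum of message coefficients)/(1 - sum of activity-lag coefficients). The means over 80 people were compared with zero by a one-sample t-test. True effect zero throughout.

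| Scenario | Mean response, min per message |
|---|---|
| Waking epochs, 09:00-21:00, flat activity | -0.03 to +0.01 |
| Same, half activity early and late | +0.18 to +0.20 |
| Same, afternoon peak | +0.30 to +0.36 |
| Same, peaks at 07-09 and 17-19 | -0.27 to -0.23 |
| Afternoon peak, delivery 07-11 or 19-23 | -0.42 to -0.37 |
| All 96 epochs, 09:00-21:00 (flat or afternoon peak) | +0.53 to +0.85 |
| Afternoon peak, delivery window plus lag only, no clock term | +0.17 to +0.20 |
| Hourly clock term, six scenarios | -0.05 to +0.04 |
| All epochs, 24-hour delivery | -0.02 to +0.01 |

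A second simulation used other profiles, 126 weekdays and delivery 08:00-20:00. Over all epochs without a clock term it gave about +1.2 (midday), +0.9 (evening) and -0.1 (early morning). Limiting epochs to 08:00-22:00 left about +0.2, +0.05 and -0.08. An epoch-of-day term gave -0.01 to +0.02, with 6 of 108 tests rejected (5.6%). A third run with 09:00-21:00 delivery gave about +0.3 (afternoon peak), -0.37 (two peaks) and +0.5 (night as zero).

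**How far the sizes can be trusted.** In the first simulation, changing only the model order moved the afternoon-peak result from +0.17 to +0.20 (1 lag, 1 h) up to +0.54 to +0.59 (4 lags, 4 h). Rejection rates are also fragile. With estimation SE 0.044 and an assumed between-person SD s of true responses, SE = sqrt(0.044² + s²/80). This is 0.071, 0.120 and 0.228 for s = 0.5, 1 and 2. A shift of +0.18 to +0.20 is then rejected about 71-79%, 32-38% and 12-14% of the time, against 85% with s = 0. The bias in the mean remains; the near-certainty of a false result does not.

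**The case against.** The strongest reply is that section 9.4.2 is not a full list of model inputs. Weather is a planned input in sections 1.1 and 2.1, and 9.4.2 omits that too. The synopsis mentions temporal conditions, so clock time may be intended. A reader might infer that the sponsor has chosen a model without clock time and that the primary results are therefore confounded. The documents do not support that: they leave the model under-specified, and they do not exclude a clock term. This stands, and it is why the conclusion is conditional. Section 2.1's remark that "the timing and magnitude of responses varied" does not settle it, since it can mean the delay of a response rather than the hour of the day.

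Delivery hours are also unproven. A random schedule over 24 hours would carry no bias, and the hours may be given in material not available here, such as the schema listed as section 1.2. Part-day delivery is an inference: phones are carried while awake (section 5.1), and acknowledgement within 30 minutes is paid for and monitored (sections 5.5 and 6.4). Acknowledgement is not required. The inference is reasonable, no more.

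A dynamic model also carries recent activity forward, which might be thought to absorb the daily rhythm. It did not with 1, 2 or 4 activity lags.

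Daytime non-wear was not simulated. Only night epochs scored as zero were, so no size can be claimed for it.

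Finally, a reader might infer that the tests against zero are the wrong tests and that library contrasts should replace them. They should not: section 9.1 asks about a message versus no message, and no section names Inspirational Quotes as a control.

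**Conclusion.** The point holds conditionally, with medium confidence. If messages are sent in only part of the day and activity varies over the analysed epochs, a person-specific model with weekday/weekend as its only time factor attributes hour-of-day differences to messages. The sign depends on whether sending falls in the more or the less active hours. Randomised number and content do not protect the tests against zero. An hourly baseline or 24-hour delivery removes the problem; restricting the epochs alone does not.

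No size should be carried forward. The false responses ranged from about -0.4 to +1.2 min per message across assumed profiles, windows and model orders, and the rejection rates assume that everyone responds identically. Nor does the text show that this trial's results are biased. It shows that the plan as written does not rule the bias out, and that ruling it out is cheap.

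**What to change.** In section 9.4.2:

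1. Include a time-of-day baseline, such as hourly terms, in every person-specific model. This is the essential part. Centring each message input on its sending probability at that clock time is an alternative.
2. State or cite the hours in which messages could be sent.
3. Limit the fit to waking epochs in which a message could be sent, plus the modelled lag. Treat sleep and unworn epochs as missing rather than zero where epoch-level wear data exist. Section 6.2.1 says wear is tracked but not at what resolution; if only daily wear is held, say so and apply the waking-hours limit.

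Keep the tests against zero for the section 9.1 hypothesis. As an optional supporting analysis, add within-person contrasts of Move More and of Sit Less against Inspirational Quotes, on weekdays and weekends. Content randomisation protects these: in the first simulation they stayed between -0.06 and +0.05 min in every scenario. They estimate an effect relative to a quote message, so they answer a different question.

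**Cost.** Wording and refitting. Hourly terms over 16 waking hours add 15 parameters. Even on weekends, 26 weeks give 52 × 64 = 3,328 waking epochs per person before non-wear. The contrasts are less precise if estimation noise dominates: the variance ratio is (1/0.4 + 1/0.2)/(1/0.4) = 3, an SE ratio of 1.73. With real between-person variation the ratio could be lower, and the documents give no SD to settle it.

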#### 9.4.3 ANALYSIS OF THE SECONDARY ENDPOINT(S)

N/A

---

#### 9.4.4 SAFETY ANALYSES

N/A

---

#### 9.4.5 BASELINE DESCRIPTIVE STATISTICS

N/A

---

#### 9.4.6 PLANNED INTERIM ANALYSES

N/A

---

#### 9.4.7 SUB-GROUP ANALYSES

N/A

---

#### 9.4.8 TABULATION OF INDIVIDUAL PARTICIPANT DATA

N/A

---

#### 9.4.9 EXPLORATORY ANALYSES

N/A

---

### 10 SUPPORTING DOCUMENTATION AND OPERATIONAL CONSIDERATIONS

---

#### 10.1 REGULATORY, ETHICAL, AND STUDY OVERSIGHT CONSIDERATIONS

---

### 10.1.1 INFORMED CONSENT PROCESS

---

#### 10.1.1.1 CONSENT/ASSENT AND OTHER INFORMATIONAL DOCUMENTS PROVIDED TO PARTICIPANTS

*This section should demonstrate that the consent form contains all required regulatory elements. List all consent and/or assent documents and materials submitted with this protocol. Include consent and/or assent forms, printed or web-based materials, phone scripts and any other related material.*

*If needed, describe special documents or materials (e.g., Braille, another language, audio recording).*

*Example text provided as a guide, customize as needed:*

Consent forms describing in detail the study intervention, study procedures, and risks will be given to the participant and written documentation of informed consent will be completed prior to starting the study intervention. The following consent materials are submitted with this protocol: informed consent document.

---

#### 10.1.1.2 CONSENT PROCEDURES AND DOCUMENTATION

Written informed consent will be a two-step process. Written informed consent for the run-in portion of the study will take place at the initial study visit. Written informed consent for the intervention portion of the study will take place at the second study visit upon verification of a participant's activity levels that are less than 150 minutes of moderate- or greater intensity PA per week.

---

### 10.1.2 STUDY DISCONTINUATION AND CLOSURE

This study may be temporarily suspended or prematurely terminated if there is sufficient reasonable cause. Written notification, documenting the reason for study suspension or termination, will be provided by the suspending or terminating party to study participants, funding agency, and regulatory authorities. If the study is prematurely terminated or suspended, the Principal Investigator (PI) will promptly inform study participants, the Institutional Review Board (IRB), and sponsor/funding agency and will provide the reason(s) for the termination or suspension. Study participants will be contacted, as applicable, and be informed of changes to study visit schedule.

Circumstances that may warrant termination or suspension include, but are not limited to:

- Determination of unexpected, significant, or unacceptable risk to participants
- Demonstration of efficacy that would warrant stopping
- Insufficient compliance of study staff to the protocol (ie, significant protocol violations)
- Data that are not sufficiently complete and/or evaluable

The study may resume once concerns about safety, protocol compliance, and data quality are addressed, and satisfy the funding agency, sponsor, IRB, or other relevant regulatory or oversight bodies (OHRP, DSMB).

#### 10.1.3 CONFIDENTIALITY AND PRIVACY

Participant confidentiality and privacy is strictly held in trust by the participating investigators, their staff, the safety and oversight monitor(s), and the sponsor(s) and funding agency. This confidentiality is extended to the data being collected as part of this study. Data that could be used to identify a specific study participant will be held in strict confidence within the research team. No personally-identifiable information from the study will be released to any unauthorized third party without prior written approval of the sponsor/funding agency.

All research activities will be conducted in as private a setting as possible.

The study monitor, other authorized representatives of the sponsor or funding agency, representatives of the Institutional Review Board (IRB), regulatory agencies or representatives from companies or organizations supplying the product, may inspect all documents and records required to be maintained by the investigator.

The study participant's contact information will be securely stored at the research site for internal use during the study. At the end of the study, all records will continue to be kept in a secure location for as long a period as dictated by the reviewing IRB, Institutional policies, or sponsor/funding agency requirements.

##### Measures Taken to Ensure Confidentiality of Data Shared per the NIH Data Sharing Policies

It is NIH policy that the results and accomplishments of the activities that it funds should be made available to the public (see <https://grants.nih.gov/policy/sharing.htm>). The PI will ensure all mechanisms used to share data will include proper plans and safeguards for the protection of privacy, confidentiality, and security for data dissemination and reuse (e.g., all data will be thoroughly de-identified and will not be traceable to a specific study participant). Plans for archiving and long-term preservation of the data will be implemented, as appropriate.

##### Certificate of Confidentiality

To further protect the privacy of study participants, the Secretary, Health and Human Services (HHS), has issued a Certificate of Confidentiality (CoC) to all researchers engaged in biomedical, behavioral, clinical or other human subjects research funded wholly or in part by the federal government. Recipients of NIH funding for human subjects research are required to protect identifiable research information from forced disclosure per the terms of the NIH Policy (see <https://humansubjects.nih.gov/coc/index>). As set forth in 45 CFR Part 75.303(a) and NIHGPS Chapter 8.3, recipients conducting NIH-supported research covered

by this Policy are required to establish and maintain effective internal controls (e.g., policies and procedures) that provide reasonable assurance that the award is managed in compliance with Federal statutes, regulations, and the terms and conditions of award. It is the NIH policy that investigators and others who have access to research records will not disclose identifying information except when the participant consents or in certain instances when federal, state, or local law or regulation requires disclosure. NIH expects investigators to inform research participants of the protections and the limits to protections provided by a Certificate issued by this Policy.

---

#### 10.1.4 FUTURE USE OF STORED SPECIMENS AND DATA

Data collected for this study will be analyzed and stored in secure cloud storage provided by The Pennsylvania State University.

When the study is completed, access to study data will be provided through the principal investigator.

---

